11.11 Appendix 11. New York Heart Association Functional Classification

1. Class I No limitation of physical activity. Ordinary physical activity does not cause undue fatigue, palpitation or dyspnea.
2. Class II Slight limitation of physical activity. Comfortable at rest, but ordinary physical activity results in fatigue, palpitation or dyspnea.
3. Class III Marked limitation of physical activity. Comfortable at rest, but less than ordinary activity causes fatigue, palpitation or dyspnea.
4. Class IV Unable to carry out any physical activity without discomfort. Symptoms of cardiac insufficiency may be present even at rest. If any physical activity is undertaken, discomfort is increased.

11.12 Appendix 12. Adaptive Design

The guidelines described in Section 4.1 for dose escalation or de-escalation to the next dose level are determined by a mTPI-2 algorithm (Guo et al, 2017). The mTPI-2 algorithm employs a simple beta-binomial Bayesian model. Let p_T be the target toxicity level and $(p_T - \epsilon_1, p_T + \epsilon_2)$ be the equivalence toxicity interval denoted as EI. The unit toxicity interval $(0, 1)$ is divided into subintervals with equal length given by $(\epsilon_1 + \epsilon_2)$. Let the under-dosing intervals (LI) denote for a set of intervals below EI, and the overdosing intervals (HI) for a set of intervals above EI. The 3 types of dosing intervals (EI, LI, HI) are associated with 3 different dose-escalation decisions. The LI correspond to a dose escalation (E), the HI correspond to a dose de-escalation (D), and proper dosing intervals (EI) correspond to staying at the current dose (S). This study design uses a target toxicity level, p_T of 30%, and EI of (25%, 35%).

Decision rules are based on the unit probability mass (UPM) calculated on these equal-length intervals. Given an interval and a probability distribution, the UPM of that interval is defined as the probability of the interval divided by the length of the interval. The mTPI-2 design calculates the UPMs for the each of equal-length dosing intervals. If the interval with the largest UPM is from LI, EI or HI, then the corresponding dose decision would be E, S, or D, respectively.

A dose level will be considered unsafe, with no additional subjects enrolled at that dose level, if it has an estimated 95% or more probability of exceeding the target DLT rate p_T (ie, $P[\text{DLT} > p_T \mid \text{data}] > 95\%$). Based on this rule, the following instances would result in a dose level being considered unsafe.

- 3 or more DLTs in ≤ 4 subjects
- 4 or more DLTs in ≤ 6 subjects
- 5 or more DLTs in ≤ 9 subjects
- 6 or more DLTs in 10 subjects

After the escalation phase is completed, final DLT rates at each dose level will be estimated by isotonic regression (Ji et al, 2010). The weighted least squares regression model will assume monotonic non-decreasing DLT rates with increasing dose and use the empirical (observed) DLT rates at each dose level as responses and dose level sample sizes as weights, along with the pool adjacent violators algorithm (PAVA) to estimate the DLT rate at each dose level. Given the DLT estimates for each dose level, the MTD will be selected from all tried dose levels that have not been previously declared to be unsafe with a decision according to the mTPI decision table. With this

constraint, the MTD will be determined as the dose level with the DLT estimate closest to the target toxicity level of 30%.

Amendment 7

**Protocol Title: A Phase 1b Study Evaluating the Safety, Tolerability,
Pharmacokinetics and Efficacy of Delta-like Protein 3 Half-life Extended Bispecific
T-cell Engager AMG 757 in Subjects with De Novo or Treatment Emergent
Neuroendocrine Prostate Cancer**

Amgen Protocol Number Tarlatamab (AMG 757) 20200040

EU CT Number 2024-513316-10

NCT Number NCT04702737

Amendment Date: 21 June 2024

Rationale:

This protocol has primarily been amended to include the following changes:

- Update details about Protocol Approver and Key Sponsor Contact
- Remove EudraCT Number from the title page of the protocol.
- Align the protocol with the latest clinical protocol template.
- Remove 2 and 3 step dosing of cycle 1 scheduling tables (i.e. Table 1-1), Schedule of Activities tables (i.e. Table 1-3, Table 1-4), overall design Section 4.1 and step dosing Section 6.2.1.2.1.
- Update footnote e and ff for SoA table.
- Update Safety Follow-Up visit from 42 (\pm 5) days to 60 (+5) days.
- Remove Section 2.3.1.4 and Section 6.8.1 sucrose medicated renal impairment.
- Update provision of investigational product in Section 4.4.1
- Update male subjects use of contraception, use of condom and donating sperm timing from 132 days after the last dose of tarlatamab to 60 day after the last dose of tarlatamab.
- Update the title and content of Noninvestigational Products/Auxiliary Medicinal Products Section to be in accordance with European Union Clinical Trials

Regulation (EU CTR) and modify the wording “protocol-required therapy” to “noninvestigational product(s)/auxiliary medicinal product(s)”

- Remove Section 6.1.3, Other Protocol Required Therapies as this section is not applicable in this study.
- Remove live and live-attenuated vaccines during study drug therapy from exclusion criteria.
- Update serious and fatal serious adverse events collection, recording, and reporting period to sponsor to be immediately and no later than 24 hours rather than within 24 hours.
- Add Section 8.2.3.4.2, Hypersensitivity as other safety measure.
- Add Serious Breach in Appendix 3, SAE related information, Results Reporting in the protocol to align with the latest clinical protocol template.
- Other Safety Findings/Special Situations language has been added to Section 8.2.4.6 and Section 11.4 (Appendix 4).
- Update electronic Serious Adverse Event Contingency Form in Appendix 4. Safety Events: Definitions and Procedures for Recording, Evaluating, Follow-Up and Reporting, Figure 11-1. Sample Electronic Serious Adverse Event Contingency Form.
- Update Section 11.7, Appendix 7. Reporting and Management of potential Hepatotoxicity.
- Update Section 11.8, Response Evaluation Criteria in Solid Tumors Version 1.1 (RECIST v1.1) Evaluation of Non-target Lesions table.

Amendment 6

Protocol Title: A Phase 1b Study Evaluating the Safety, Tolerability, Pharmacokinetics and Efficacy of Delta-like Protein 3 Half-life Extended Bispecific T-cell Engager Tarlatamab in Subjects with De Novo or Treatment Emergent Neuroendocrine Prostate Cancer (DeLLpro-300)

Amgen Protocol Number (AMG 757) 20200040

EudraCT Number 2020-003508-15

NCT Number: NCT04702737

Amendment Date: 29 September 2022

Rationale:

The protocol is being amended to address further biomarker exploration with the addition of a prospectively selected delta-like protein 3 (DLL3) + neuroendocrine prostate cancer (NEPC) cohort (n ~ 40 subjects). Applicable sections of the protocol are being modified to address this addition to the study and the subsequent analyses associated with the new cohort. Changes including, but not limited to, the following are being incorporated into the protocol:

- Added language to incorporate prospective DLL3 selection in the eligibility criteria, biomarker assessment and all other related sections
- Added language to align aspects of data collection and monitoring across the tarlatamab program
- Key safety information updated to include immune effector cell associated neurotoxicity syndrome and reference to the investigator brochure for complete information
- Removal of schedule of activities (SOA) tables for 2-step and 3-step-dosing and the inclusion of a SOA table for extended intravenous (eIV) dosing
- Editorial changes (including typographical, grammatical, and formatting) have been made throughout the document

Amendment 5

Protocol Title: **A Phase 1b Study Evaluating the Safety, Tolerability, Pharmacokinetics and Efficacy of Delta-like Protein 3 Half-life Extended Bispecific T-cell Engager AMG 757 in Subjects with De Novo or Treatment Emergent Neuroendocrine Prostate Cancer**

Amgen Protocol Number AMG 757 20200040

EudraCT number: 2020-003508-15

NCT Number: NCT04702737

Amendment Date: 20 December 2021

Rationale:

This protocol is being amended to address site shortages of tocilizumab. Applicable sections of the protocol are being modified to clarify the use of siltuximab in place of tocilizumab for the treatment of potential cytokine release syndrome (CRS) during a treatment-related adverse event. Tarlatamab clinical experience and safety guidance is being updated. Language is being included throughout to update/clarify the protocol. Changes including, but not limited to, the following are being incorporated into the protocol:

- Added language to include neutropenia as a risk following study treatment administration and guidance for treatment of neutropenia.
- Criteria for use of siltuximab in place of tocilizumab, justification for the proposed dose and schedule, safety stopping rules, and guidance throughout the protocol are being included.
- Table 6-4, “Tarlatamab Dose Modification Guidelines for Adverse Events” is being added.
- Updated language on recording and reporting of serious adverse events.
- Administrative, typographical, and editorial changes have been made throughout the protocol.

Amendment 4

Protocol Title: A Phase 1b Study Evaluating the Safety, Tolerability, Pharmacokinetics and Efficacy of Delta-like Protein 3 Half-life Extended Bispecific T-cell Engager AMG 757 in Subjects with De Novo or Treatment Emergent Neuroendocrine Prostate Cancer

Amgen Protocol Number (AMG 757) 20200040

Amendment Date:

19 April 2021

Rationale:

The protocol is being updated:

- Due to updates in the mean half-life estimate for AMG 757 [REDACTED] the time to the safety follow up visit from the last dose of AMG 757 and the guidance on contraception for males and female partners have been updated.
 - Updated the Secondary Endpoints to include Disease Control Rate
 - To align with the ongoing first in human (FIH) study (study 20160323), additional exclusion criteria have been added, including "Has evidence of interstitial lung disease or active, non-infectious pneumonitis" and "Live vaccine therapy within 4 weeks prior to study drug administration".
 - To allow for subjects with recurrent Grade 3 abnormalities that are not considered clinically significant or that can be managed with supportive care, the protocol has been updated to allow subjects with recurrent Grade 3 laboratory parameters not considered clinically relevant or recurrent non-febrile Grade 3 neutropenia which resolves with supportive care to grade ≤ 1 or to baseline values within 3 weeks to remain on study. Additionally the protocol has been updated to allow for the use of growth factors, such as erythropoiesis-stimulating proteins as well as granulocyte colony stimulating factor (G-CSF), throughout the study as needed.
 - Removed 1 Exclusion criterion meant for female subjects of childbearing potential, since this study will allow only male subjects.
- [REDACTED]
- Updated section 2.2.2.3 (Background Clinical Experience with Amgen Investigational Product AMG 757), based on emerging clinical data from the ongoing FIH study (20160323).
 - To allow for the subject's legally authorized representative to sign the consent on their behalf.
 - The number of investigative sites was increased from approximately 20 to approximately 25.

- 
- Clarified that ECG measurements from this clinical study are performed as part of standard of care for routine safety monitoring, rather than for statistical analysis.
 - Updated the Dose Cohort Levels that may be explored in Table 4-1 based on results from study 20160323 in small cell lung cancer
 - Updated the toxicity interval in the mTPI-2 design. Updated Escalation/De-escalation guidelines (Table 4-2) and the decision rule when a dose level will be considered unsafe based on the mTPI2 design.
 - Added a table of operating characteristics for the mTPI2 design (Table 4-3), so that it is clear how this design performs under given hypothetical true DLT rates.
 - Added Management and restrictions for Covid-19 and vaccines
 - To make editorial and formatting changes as applicable.

Amendment 3

Protocol Title: A Phase 1b Study Evaluating the Safety, Tolerability, Pharmacokinetics and Efficacy of Delta-like Protein 3 Half-life Extended Bispecific T-cell Engager AMG 757 in Subjects with De Novo or Treatment Emergent Neuroendocrine Prostate Cancer

Amgen Protocol Number (AMG 757) 20200040

Amendment Date: 10 December 2020

Rationale:

The protocol is being updated:

- To add IV hydration at week 3 day 15 in Tables 1-2 and 1-3.
- To update Table 1-6 to include new footnotes and a central and biomarker laboratory test.
- To correct the abbreviations in the exploratory endpoints.
- To add safety language related to Coronavirus Disease 2019 (COVID-19) in the risk-benefit section.
- To clarify on the laboratory assessment collection timepoint.
- To remove the list of procedures performed at safety follow-up period section.
- To clarify that Mini-Mental Status Examination (MMSE) Version 2 will be performed as a part of the clinical evaluation.
- To remove the language stating that radiological imaging assessment will be performed every 12 weeks for response assessment only in the dose exploration phase.
- To clarify the sponsor responsibility for reporting of serious adverse events.
- To remove the language about requirement of local laboratory results only in the absence of central laboratory results in Appendix 11.2.
- To further clarify on the Dose Level Review Team (DLRT) recommendations on premedication based on emerging results from an ongoing first-in-human (FIH) study (20160323) in Appendix 11.3.
- To make editorial and formatting changes as applicable.

Amendment 2

Protocol Title: A Phase 1b Study Evaluating the Safety, Tolerability, Pharmacokinetics and Efficacy of Delta-like Protein 3 Half-life Extended Bispecific T-cell Engager AMG 757 in Subjects with De Novo or Treatment Emergent Neuroendocrine Prostate Cancer

Amgen Protocol Number (AMG 757) 20200040

Amendment Date: 09 October 2020

Rationale:

This protocol is being updated:

- To add prophylaxis with intravenous (IV) hydration immediately after doses in cycle 1
- To restrict the [REDACTED] collection timepoints at day 1 of cycles 1 and 4, and at end of treatment (EOT).
- To make editorial and formatting changes as applicable.

Amendment 1

		Section 5.3: Updated definition language for Best Overall Response, Disease Control Rate, Duration of Response, Objective Response Rate, Radiographic Progression and Radiographic Progression-free survival.
		Section 5.4: Updated definition language for
		Section 6.2: Updated language for Safety Analysis Set definition.
		Section 6.6: Updated text in Interim Efficacy Analysis Set definition from 'day 1' to 'study day 1'.
		Section 6.7: Updated language for DLT Analysis Set definition. Added following analysis sets: RECIST 1.1 Evaluable by Central Reviewer Analysis Set, RECIST 1.1 Evaluable by Investigator Assessment
		Analysis Set, Evaluable Based on Central Laboratory Data Analysis Set, Evaluable Based on Local Laboratory Data Analysis Set,
		Section 9.4: Added clarification that ethnicity will be reported only for subjects

Date: 24 March 2023 Page 3 of 53

with race as 'white'. Removed 'Tobacco use'. Updated text from 'Sum of diameters of target lesions at baseline (mm)' to 'Sum of diameters of target lesions at baseline based on investigator assessment (mm)'.

Section 9.5.2: Added details for use of central data and/or local data for primary analysis.

Table 9-1: Updated text 'quartiles' to 'percentiles'. Updated analysis set for the following endpoints: Objective Response, Duration of Response, Disease Control Rate.

Section 9.5.3: Added details for use of central data and/or local data for primary analysis.

Table 9-2: Updated analysis set for the following endpoints:

Section 9.6.8: Updated section to present only number of doses, cumulative dose (mg), relative dose intensity (%), treatment duration (weeks) for exposure summary.

Section 10: Added details for changes from protocol-specified analysis.

Appendix B: Updated appendix title from 'Censoring Rules for Progression Free Survival' to 'Censoring Rules for Radiographic Progression-free Survival'.

Table 14-2: Updated table title from 'Censoring Rules for Progression Free Survival' to 'Censoring Rules for Radiographic Progression-free Survival'. Updated language for censoring rules.

Table 9-3.	Safety Endpoint Summary Table	39
Table 14-1	. Imputation Rules for Partial or Missing Start Dates	45
Table 14-2	. Censoring Rules for Radiographic Progression-free Survival	47
Table 14-3	. BOR per RECIST 1.1 where Confirmation of CR/PR is Required	49
Table 14-4	BOR Derivation Step	51
Table 14-5	Bone Progression Status per PCWG3	52
Table 14-6	Radiographic Progression by RECIST 1.1 with PCWG3 Modifications	52
	List of Figures	
Figure 7-1	Decision Matrix for Continuous Monitoring of ORR	30

Protocol Number: 20200040
Date: 24 March 2023 Page 9 of 53

List of Abbreviations

Abbreviation	Explanation
AE	Adverse event
ВМІ	Body mass index
BOR	Best overall response
CI	Confidence intervals
COVID-19	Novel coronavirus disease
CR	Complete response
CRF	Case report form
CRS	Cytokine release syndrome
СТ	Computed tomography
CTCAE	Common terminology criteria for adverse events
DCO	Data cut-off
DCR	Disease control rate
DOR	Duration of response
DLL3	Delta-like protein 3
DLRM	Dose level review meeting
DLRT	Dose level review team
DLT	Dose limiting toxicity
ECG	Electrocardiogram
ECOG	Eastern cooperative oncology group
EI	Equivalence toxicity interval
ĺ	
EOS	End of study
EOT	End of treatment
FIH	First-in-human
GSO-DM	Global study operations-data management
HI	Overdosing intervals
IPD	Important protocol deviation
IV	Intravenous
IV	IIIII aveiious

Date: 24 March 2023 Page 10 of 53

IP Investigational product

KM Kaplan-Meier

LI Under-dosing intervals

LTFU Long term follow-up

MedDRA The medical dictionary for regulatory activities

MRI Magnetic resonance imaging

MTD Maximum tolerated dose

mTPI-2 Modified toxicity probability interval design

NE Not evaluable

NEB No evidence of bone lesion

NEPC Neuroendocrine prostate cancer

NP Not performed

OR Objective response

ORR Objective response rate

OS Overall survival

PAVA Pool adjacent violators algorithm
PCWG3 Prostate cancer working group 3

PD Pharmacodynamic
PD Progressive disease

PDc Confirmed PD PDu Unconfirmed PD

PD-1 (L1) Programmed cell death protein 1 (Ligand-1)

PFS Progression-free survival

PK Pharmacokinetic
PR Partial response

Q2W Every 2 weeks

RECIST Response evaluation criteria in solid tumors

RP2D Recommended phase 2 dose

RR Relapsed/refractory

SAP Statistical analysis plan

SD Stable disease

SFU	Safety follow-up
SUV	Standardized uptake value
TEAE	Treatment-emergent adverse event
TLS	Tumor lysis syndrome
TNM	Tumor, node, metastatic
TRAE	Treatment-related adverse event
UPM	Unit probability mass
WHO	World health organization

Date: 24 March 2023 Page 12 of 53

1. Introduction

The purpose of this Statistical Analysis Plan (SAP) is to provide details of the statistical analyses that have been outlined within the protocol amendment 6 for study 20200040, **Tarlatamab (AMG 757)** dated 29 September 2022. The scope of this plan includes the interim analyses, the primary analysis and the final analysis that are planned and will be executed by the Amgen Global Biostatistical Science department unless otherwise specified.

2. Objectives, Endpoints/Estimands and Hypotheses

2.1 Objectives and Endpoints/Estimands

Objectives	Endpoints		
Primary	Primary		
 Evaluate the safety and tolerability of tarlatamab 	Treatment-emergent adverse events, treatment-related adverse events, and changes in vital signs, electrocardiogram (ECG), and clinical laboratory tests		
 Determine the maximum tolerated dose (MTD) or recommended phase 2 dose (RP2D) 	Dose limiting toxicities (DLTs)		
Secondary			
 Evaluate anti-tumor activity of tarlatamab as assessed by additional measures 	Objective response (OR) per Response Evaluation Criteria in Solid Tumors (RECIST 1.1)		
	 Duration of response (DOR) per RECIST 1.1 		
	 Radiographic progression-free survival (PFS) per RECIST 1.1 with Prostate Cancer Working Group 3 (PCWG3) modifications 		
	Overall Survival (OS)		
	Disease Control Rate (DCR) per RECIST 1.1		
Characterize the pharmacokinetics (PK) of tarlatamab	PK parameters for tarlatamab following intravenous (IV) administration including, but not limited to, maximum serum concentration (Cmax), minimum serum concentration (Cmin), area under the concentration-time curve		

Date: 24 March 2023 Page 13 of 53

[figure not shown]
	(AUC) over the dosing interval, accumulation ratio, and half-life (t1/2)
--	--

Estimand(s) for Primary Objective(s)

Not applicable for this study.

Estimand(s) for Secondary Objective(s)

Not applicable for this study.

Date: 24 March 2023 Page 14 of 53

2.2 Hypotheses and/or Estimations

No statistical hypotheses will be tested.

3. Study Overview

3.1 Study Design

This is an open label phase 1b study evaluating tarlatamab monotherapy. Tarlatamab will be administered as a short-term intravenous (IV) infusion every 2 weeks (Q2W) (with step dosing) in a 28-day cycle as monotherapy in subjects with de novo or treatment-emergent Neuroendocrine Prostate Cancer (NEPC).

The study will consist of 2 parts: dose exploration (Part 1), dose expansion (Part 2,

Dose Exploration (Part 1)

The dose exploration part of the study will enroll up to 20 subjects with relapsed/refractory NEPC. At the time of initiation of the study, the starting dose will be the highest dose deemed safe and tolerable in the ongoing phase 1 trial of tarlatamab in subjects with Small Cell Lung Cancer (SCLC) (Note: based on emerging safety data from Study 20160323, the starting dose may be lower than the highest dose deemed safe and tolerable). The planned highest dose in this study is not anticipated to exceed the maximum tolerated dose (MTD) as established in the ongoing Study 20160323.

Dose exploration will begin with treating 3 to 4 subjects at the Dose Level 1. The study dose limiting toxicity (DLT) period is 28 days. Once all subjects enrolled at a certain dose level are DLT evaluable, a dose level review team (DLRT) will convene. For any dose level, and depending on observed safety data, the following recommendation may occur:

- dose de-escalation to the next lowest dose level
- additional enrollment to the current dose level
- dose escalation to the next highest dose level

Dose escalation/de-escalation recommendations will be guided by a modified toxicity probability interval design (mTPI-2) model (Guo et al, 2017) with a target toxicity probability of 0.3 (protocol Table 4-2) and equivalence toxicity interval of (25%, 33%). The operating characteristics in protocol Table 4-3 provide the probability of selecting each dose level and the expected number of treated patients at each dose level for given hypothetical true DLT rates.

If late onset of adverse events occur during a cohort, the DLRT may adaptively re-consider the doses evaluated within a cohort for subsequent dosing and/or possibly trigger a de-

Date: 24 March 2023 Page 15 of 53

escalation or withholding of additional doses in subsequent cohorts. The MTD will be estimated using isotonic regression (Ji et al, 2010) and the MTD will be the dose level with the estimated DLT rate closest to 0.30. In order to consider a certain Dose Level as the MTD at least 6 DLT evaluable subjects must be enrolled at that dose level. No more than 10 DLT evaluable subjects will be enrolled at any specific dose level in dose exploration phase.

At the time of enrollment, the dose-escalation phase (Part 1) will be eliminated if the recommended phase 2 dose (RP2D) or MTD has been selected in the ongoing phase 1 trial of tarlatamab in small cell lung cancer. Tarlatamab will then be dosed based upon the RP2D/MTD selected in small cell lung cancer trials. Note: if Part 1 is initially eliminated based upon the RP2D/MTD selection in the phase 1 trial in small cell lung cancer, dose escalation may be opened in the future to explore additional dose(s) and dosing schedule(s) as described above.

Dose Expansion (Part 2)

Once the RP2D/MTD has been determined, enrollment will commence in the dose expansion phase to confirm the safety and tolerability of the selected dose and to further evaluate anti-tumor activity.

One or more dosing schedules as described in Part 1 may be pursued in parallel during the expansion phase. Dosing schedules involving as noted in protocol Table 1-3 may be pursued in parallel or instead of the step dosing approach based on recommendations from the emerging safety, efficacy, and PK/PD data from the ongoing phase 1 trial in SCLC.

Based on emerging data from the tarlatamab monotherapy in this indication and emerging data from other trials with tarlatamab, the protocol may be amended to include a combination of tarlatamab with anti-PD-1 (L1) agent.

The overall study design is described by a study schema in protocol section 1.2.

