Dose exploration will begin with treating 3 to 4 subjects at the Dose Level 1 (dose level 1 is the highest dose deemed safe and tolerable in ongoing phase 1 trial of tarlatamab in subjects with small cell lung cancer [Note: based on emerging safety data from Study 20160323, the starting dose may be lower than the highest dose deemed safe and tolerable]). The study DLT period is 28 days. Once all subjects enrolled at a certain dose level are DLT evaluable, a DLRT will convene. For any dose level, and depending on observed safety data, the following recommendation may occur: 1) dose de-escalation to the next lowest dose level, 2) additional enrollment to the current dose level, 3) dose escalation to the next highest dose level. Dose escalation/de-escalation recommendations will be guided by a modified toxicity probability interval design (mTPI-2) model (Guo et al, 2017) with a target toxicity probability of 0.3 (Table 4-2) and equivalence toxicity interval of (25%, 35%). The operating characteristics in Table 4-3 provide the probability of selecting each dose level and the expected number of treated patients at each dose level for given hypothetical true DLT rates.

Table 4-2. Guideline for Escalation/De-escalation

Number of Evaluable Subjects	Number of DLTs	Decision
3-4	0	E ^c
	1	S
	2	D ^b
	≥ 3	DU
5	0-1	E ^c
	2-3	D ^b
	≥ 4	DU
6	0-1	E ^c
	2	S
	3	D ^b
	≥ 4	DU
7-8	0-1	E ^c
	2	S
	3-4	D ^b
	≥ 5	DU
9	≤ 2	E ^c
	3	S
	4	D ^b

Number of Evaluable Subjects	Number of DLTs	Decision
	≥ 5	DU
10 ^a	≤ 2	E ^c
	3	S
	4-5	D ^b
	≥ 6	DU

DLT = dose-limiting toxicity; D = de-escalate to the next lower dose level (can be re-escalated back based on future data); DU = the current dose is unacceptably toxic and can't be re-escalated; E = escalate to the next higher dose; S = stay at the current dose.

^a As appropriate to better understand safety profile for a dose level, the number of evaluable subjects may be expanded up to 10.

^b De-escalate guideline applies only when enrollment is allowed to a lower dose level.

^c If a higher dose level is not allowed, then the current dose level can be expanded.

Table 4-3. Operating Characteristics for mTPI-2 Model

	Dose 1	Dose 2	Early Stopping Probability
Scenario 1			
DLT probability	30%	44%	
Selection probability	67%	20%	13%
Expected # Patients	9	4	
Scenario 2			
DLT probability	13%	30%	
Selection probability	27%	72%	1%
Expected # Patients	7	9	

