3.3 Adaptive Design

The guidelines described in protocol Section 4.1 for dose escalation or de-escalation to the next dose level are determined by using a mTPI-2 algorithm (Guo et al, 2017). The mTPI-2 algorithm employs a simple beta-binomial Bayesian model. Let p_T be the target toxicity level and $(p_T - \epsilon 1, p_T + \epsilon 2)$ be the equivalence toxicity interval denoted as EI. The unit toxicity interval (0, 1) is divided into subintervals with equal length given by $(\epsilon 1 + \epsilon 2)$. Let the under-dosing intervals (LI) denote for a set of intervals below EI, and the overdosing intervals (HI) for a set of intervals above EI. The 3 types of dosing intervals (EI, LI, HI) are associated with 3 different dose-escalation decisions. The LI correspond to a dose escalation (E), the HI correspond to a dose de-escalation (D), and proper dosing intervals (EI) correspond to staying at the current dose (S). This study design uses a target toxicity level, p_T of 30%, and EI of (25%,33%). Decision rules are based on the unit probability mass (UPM) calculated on these equal-length intervals. Given an interval and a probability distribution, the UPM of that interval is defined as the probability of the interval divided by the length of the interval. The mTPI-2 design calculates the UPMs for the each of equal-length dosing intervals. If the interval with the largest UPM is from LI, EI or HI, then the corresponding dose decision would be E, S, or D, respectively.

A dose level will be considered unsafe, with no additional subjects enrolled at that dose level, if it has an estimated 95% or more probability of exceeding the target DLT rate p_T (i.e., P [DLT > p_T | data] > 95%). Based on this rule, the following instances would result in a dose level being considered unsafe.

- 3 or more DLTs in ≤ 4 subjects
- 4 or more DLTs in ≤ 6 subjects
- 5 or more DLTs in ≤ 9 subjects
- 6 or more DLTs in 10 subjects

Date: 24 March 2023 Page 17 of 53

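### The SAP states an mTPI-2 equivalence interval of (25%, 33%) where the supplied protocol states (25%, 35%); of the two, only 35% reproduces protocol Table 4-2 under an assumed Beta(1,1) prior

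*SAP*

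**What the plan says.** SAP 3.1 sets the escalation rule "with a target toxicity probability of 0.3 (protocol Table 4-2) and equivalence toxicity interval of (25%, 33", closing the interval at 33%. SAP 3.3 gives the same two bounds in its account of the algorithm. Protocol 4.1 instead has "equivalence toxicity interval of (25%, 35", closing at 35%, and Protocol 9.4.2.5 and Appendix 12 agree with it.

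The rest of the design is the same in both documents: a 30% target, a partition of (0, 1) into subintervals as wide as the equivalence interval, a decision set by the subinterval with the largest unit probability mass (UPM), and a dose declared unsafe when the posterior probability of exceeding 30% is above 95%. The lists of unsafe outcomes also agree, including "5 or more DLTs in ≤ 9 subjects". SAP Section 10, which records changes from protocol-specified analyses, lists only a change of analysis sets.

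On versions, SAP Section 1 says its analyses "have been outlined within the protocol amendment 6 for study 20200040". The supplied protocol is Amendment 7. Its amendment log records under Amendment 4: "Updated the toxicity interval in the mTPI-2 design. Updated Escalation/De-escalation guidelines (Table 4-2"), and also "Added a table of operating characteristics for the mTPI2 design (Table 4-3"). The entries for Amendments 5 to 7 do not mention the interval. The Amendment 6 entry introduces its list with "Changes including, but not limited to, the following", so that list is not exhaustive.

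**The concern.** The equivalence interval separates Stay from Escalate and De-escalate, so the two texts describe two different rules. SAP 3.1 names protocol Table 4-2 in the same sentence as its interval. If 33% does not generate that table, the sentence contradicts itself, and a statistician who programs the rule from the SAP will get decisions that disagree with the table the team uses. DLTs are the endpoint for the MTD/RP2D primary objective, so the threshold should be the same wherever it is written.

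**Working it through.** **Inputs.** Target 30%; interval (0.25, 0.35) from the protocol or (0.25, 0.33) from the SAP; equal-width partition and largest-UPM rule (Protocol 9.4.2.5, SAP 3.3); unsafe (DU) if P(p > 0.30 | data) > 0.95. Table 4-2 covers n = 3 to 10, which is 4 + 5 + … + 11 = 60 combinations of subjects and DLTs. The prior is not stated; Beta(1,1) is assumed, so x DLTs in n subjects give a Beta(1 + x, 1 + n − x) posterior with distribution function F.

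**Formula.** UPM(a, b) = [F(b) − F(a)] / (b − a).

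**Unsafe cells.** These do not depend on the interval. P(p > 0.30) is 0.969 at 3/4, 0.971 at 4/6, 0.953 at 5/9 and 0.978 at 6/10, so the printed unsafe list is reproduced.

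**Worked cell, 1 DLT in 3.** The posterior is Beta(2, 3), with F(p) = 6p² − 8p³ + 3p⁴.
- Protocol interval: F(0.25) = 0.26172, F(0.35) = 0.43702, F(0.45) = 0.60902. UPM for Stay = 0.17530/0.10 = 1.753; for the next interval up = 0.17200/0.10 = 1.720. Result: Stay, as printed.
- SAP interval: F(0.33) = 0.40148, F(0.41) = 0.54200. UPM for Stay = 0.13976/0.08 = 1.747; for the next interval up = 0.14052/0.08 = 1.757. Result: De-escalate, against the printed Stay.

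**All 60 cells.** With (25%, 35%) there are no mismatches. With (25%, 33%) there are three:

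| DLTs / n | Printed | 35%: UPM Stay vs De-escalate | 33%: UPM Stay vs De-escalate |
|---|---|---|---|
| 1/3 | Stay | 1.753 vs 1.720 | 1.747 vs 1.757 |
| 2/6 | Stay | 2.241 vs 2.158 | 2.226 vs 2.250 |
| 3/9 | Stay | 2.620 vs 2.478 | 2.594 vs 2.636 |

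All three are an observed rate of 33.3%, just above the SAP's upper bound and inside the protocol's. No cell changes at n = 4, 5, 7, 8 or 10. Reading 33% as a rounded 1/3 leaves the same three mismatches.

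**Which upper bounds fit, with the lower bound at 25%.** Bounds from 31% to 33.5% give the same three mismatches. Bounds from 33.55% to 37.5% give none. At 38%, 3/8 fails.

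**Sensitivity to the prior.** Over Beta(a, b) with a and b from 0.1 to 2.0 in steps of 0.1 (400 priors, one prior for both the interval step and the unsafe rule), 35% reproduces all 60 cells for 7 priors, Beta(1,1) among them, and 33% for none. If the unsafe rule kept Beta(1,1) and the interval step used some other prior, 4 of the 400 would fit 33% and 21 would fit 35%. The documents do not describe two priors.

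**Does protocol Table 4-3 help?** Under assumed cohorts of 3, at most 10 subjects per dose and 20 in total, simulated Scenario 1 selection (dose 1 / dose 2 / early stop) is 68.8/18.7/12.6% with 33% and 66.4/20.8/12.8% with 35%. The printed 67/20/13% lies close to both. Scenario 2 gives 27.3/72.0/0.7% and 26.2/73.2/0.6%, against a printed 27/72/1%. Table 4-3 does not discriminate between the two bounds.

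**The case against.** The strongest objection is that the supplied protocol may not be the text the SAP implements. The SAP plans about 100 subjects, about 80 of them in Part 2; the supplied protocol plans about 60, with 40 in Part 2. The Amendment 6 log entry adds a DLL3-selected cohort of about 40 and an extended-infusion schedule, and the supplied protocol shows neither. SAP 3.1 cites protocol Table 1-3 for a dosing schedule, but Table 1-3 in the supplied protocol is the imaging schedule. If Amendment 6 itself says 33%, the SAP follows its parent and had nothing to declare in Section 10.

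This stands as a limit on attribution. A reader might infer that 33% is a leftover from before Amendment 4, because the log dates the interval update there and SAP 3.1 cites the Table 4-3 added at the same time: "The operating characteristics in protocol Table 4-3 provide the probability of selecting each dose level". That inference needs a single line of amendments and a complete log. The differences above cast doubt on the first, and the Amendment 6 entry says its list is not complete. The objection does not remove the conflict between the two supplied texts, or the mismatch between 33% and the supplied Table 4-2.

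A second objection is practical. The chance of exactly 1 DLT in a cohort of 3 is 3p(1 − p)²: 29.5% at p = 0.13, 44.1% at 0.30 and 41.4% at 0.44, the rates used in Table 4-3. A reader might take these as the share of first cohorts handled differently. They are not. Footnote b of Table 4-2 restricts De-escalate to cases where a lower level is open for enrollment, which may not hold at Dose Level 1. A first cohort of 4, equally allowed, gives the same decision under both bounds. This objection stands and keeps the point minor.

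**Conclusion.** The inconsistency holds. The two supplied documents give different equivalence intervals, the SAP does not declare the difference, and the SAP's interval does not generate the supplied Table 4-2 under Beta(1,1): 3 of 60 cells change from Stay to De-escalate. The textual conflict needs no assumption. The mismatch with the table rests on the assumed prior, on the same prior serving both steps, and on Table 4-2 as printed in Amendment 7.

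It would go too far to say that 35% is the only value that yields the table, since upper bounds from about 33.6% to 37.5% do so too. The supported statement is that, of the two values written down, only 35% fits. Which document is out of step with Amendment 6 cannot be determined from what is supplied.

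Severity is minor. The three changed cells err towards caution, the dose level review team is guided by the printed table, and the isotonic-regression MTD step and the unsafe-dose rule do not use the interval. Part 1 may be eliminated altogether, although both documents allow it to be opened later.

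**What to change.** Look up the interval and Table 4-2 in Amendment 6.

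- If its Table 4-2 matches the supplied one, change (25%, 33%) to (25%, 35%) in SAP 3.1 and SAP 3.3.
- If Amendment 6 states 33%, align the interval and Table 4-2 across the protocol and the SAP so that the stated interval generates the printed table.

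In either case, state the prior for the DLT rate, so that the table can be reproduced from the text. The first branch costs one document check and two numbers in the SAP, with no rerun. The second costs a decision on which interval is intended and edits in both documents; if 33% is kept, the cells at 1/3, 2/6 and 3/9 change and Table 4-3 should be rerun.
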